after the last dose of the last study drug (except for subjects who died, withdrew consent and objected to further data collection or were lost to follow up).

There will be no formal assessment of the overall survival in this study.

Arm 1 - Part 1 (Safety Run-in of Mirdametinib in Combination with Fulvestrant)

If permitted by the acceptable safety profile of mirdametinib 4 mg BID in combination with the standard recommended dose of fulvestrant, the Part 1 in Arm 1 of the study will be conducted as a single dose level. Patients with any MAPK pathway activating alteration as listed in section 6.1 will be included in this safety run-in, however patients harboring NF1 loss of function mutations will be prioritized, at the discretion of the principal investigator.

If mirdametinib 4 mg BID in combination with the standard recommended dose of fulvestrant is not tolerated well in the initial Dose Level, then a Dose Level de-escalation will be evaluated with mirdametinib 2 mg BID in combination with the standard recommended dose of fulvestrant. The Dose Level de-escalation will be evaluated according to the 3+3 design based on the incidence of dose-limiting toxicities (DLT) and the overall safety profile of the study treatments. The DLT definitions are listed in [Section 15.3](#).

At each step of the 3+3 design, the investigators will review all available safety and PK data at the current dose level and decide about the appropriate next step. The subjects will become evaluable for the 3+3 decisions if they complete Cycle 1 and receive at least 80% of doses at their assigned mirdametinib doses and all of their fulvestrant doses, or if they exhibit a DLT in Cycle 1.

Dose Selection: We note that the dosing of mirdametinib in the most recent phase II trial⁶ is 2 mg/m² twice daily, which translates to 4 mg twice daily in an adult population. However, the aforementioned study used an intermittent 3 weeks on / 1 week off schedule. This protocol is slightly different in that we are initiating a continuous dosing schedule of mirdametinib rather than intermittent. We believe that this schedule remains quite safe given that this dose is far below the MTD (15 mg BID) at which intermittent dosing was necessary to avoid toxicity.

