At each step of the 3+3 design, the investigators will review all available safety and PK data in the current Dose Level and decide about the appropriate next step. The subjects will become evaluable for the 3+3 decisions if they complete Cycle 1 and receive at least 80% of assigned drug doses, or if they exhibit a DLT in Cycle 1.

The starting dose of mirdametinib as single agent in each Dose Level escalation will be as follows:

- Dose Level 1: **mirdametinib 4 mg BID PO**, given continuously
- Dose Level 2: **mirdametinib 6 mg BID PO**, given continuously
- Dose Level 3: **mirdametinib 8 mg BID PO**, given continuously
- The de-escalation (Dose Level -1) may evaluate **mirdametinib 3 mg BID** given continuously, and (Dose Level -1INT) may evaluate **mirdametinib 3 mg BID** given on a 3 weeks on, 1 week off schedule. These de-escalation Dose Levels will be evaluated at investigator's discretion after the higher dose of mirdametinib is not tolerated. The de-escalation Dose Levels will be started only if the benefit-risk ratio is acceptable at the investigator's opinion.

The 3+3 decisions in Part 1 of Arm 2 will be made as follows.

1. Dose Level 1 (**mirdametinib 4 mg BID PO** given continuously)
 - a. Up to 3 subjects will be treated with mirdametinib as single agent at the dose of **4 mg BID PO** given continuously.

Memorial Sloan Kettering Cancer Center
[name]
[name]

- b. If 1 of the first 3 evaluable subjects in Dose Level 1 exhibit a DLT in Cycle 1, then Dose Level 1 will be expanded (see #2 below)
- c. If 0 of the first 3 evaluable subjects in Dose Level 1 exhibit a DLT in Cycle 1, then the dose of mirdametinib as single agent will be escalated to Dose Level 2 (**6 mg BID** given continuously) (see #4 below)

2. Dose Level 1 expansion:

- a. A sufficient number of subjects will be treated with mirdametinib as single agent at the dose of **4 mg BID PO** given continuously to accrue 6 evaluable subjects.
- b. If ≤ 1 of 6 evaluable subjects in the starting Dose Level exhibit a DLT in Cycle 1, then the dose of mirdametinib as single agent will be escalated to Dose Level 2 (**6 mg BID** given continuously) (see #5 below).
- c. If ≥ 2 of the first 3 evaluable subjects or ≥ 2 of the 6 evaluable subjects in Dose Level 1 exhibit a DLT in Cycle 1, then the mirdametinib dose will be de-escalated (see #3 below).

3. Dose Level -1 (de-escalation Dose Level **3 mg BID PO** given continuously)

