13.3 Evaluable subjects

Patients who achieve sufficient compliance with the study drug intake in Cycle 1 (received at least 45 of 56 [greater than 80%] doses of mirdametinib (in Arm 1 only, also both doses of fulvestrant) **or** experience a DLT will be considered as evaluable for the assessment of the DLT rate for the particular dose level.

Additional patients should be enrolled at the same dose level as necessary to ensure an adequate number of DLT-evaluable patients.

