14.0 BIOSTATISTICS

14.1 Analysis Populations

The following analysis populations will be used:

- **DLT Evaluable Population** consists of patients who receive at least 80% of planned total doses of mirdametinib in cycle 1 (in Arm 1 only, also both doses of fulvestrant) and are observed within 28 days following the first dose of mirdametinib or patients who experience a DLT.
- **Efficacy Population**, used for the assessment of efficacy for each arm, will consist of all patients in Part 2 who received at least 1 dose of study drug and who have at least 1 post-baseline tumor assessment. Arms 1 and 2 will be analyzed separately. In addition, patients treated at the MTD in the dose escalation portion of the protocol (both arms 1 and 2) will be included in the efficacy analyses for the expansion cohorts in part 2 if they meet the requirements for efficacy population as defined above. Additionally, the RP2D will be determined pending the clinical data obtained in the dose escalation portion of the protocol. If the RP2D is less than the MTD, then patients treated at the RP2D in the dose escalation portion of the protocol (both arms 1 and 2) will be included in the

Memorial Sloan Kettering Cancer Center
[name]
[name]

efficacy analyses for the expansion cohorts in part 2 if they meet the requirements for efficacy population as defined above.

- **Pharmacokinetic Population**, used for the assessment of pharmacokinetic endpoints, will consist of all patients who have sufficient pharmacokinetic concentration data recorded to derive pharmacokinetic endpoints.
- **All treated population or safety population:** consisting of all patients who receive any amount of drug

Arms 1 and 2 will be analyzed separately throughout the study.

Arm 1

The study will follow a standard 3+3 dose escalation schema. As described previously in section 4.2, the 3+3 decisions in Part 1 of Arm 1 will be made starting with a mirdametinib starting dose level (4 mg BID PO), where subjects will be treated with mirdametinib 4 mg BID PO given continuously in combination with the recommended dose of fulvestrant. If ≤ 1 of the first 3 DLT evaluable subjects in Dose Level 1 exhibit a DLT in Cycle 1, then Dose Level 1 will be expanded. Mirdametinib dose in combination with fulvestrant will not be escalated above the 4 mg BID given continuously dose level.

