15.3 Dose Limiting Toxicities

The severity of adverse events (AEs) reviewed as potential dose-limiting toxicity (DLT) will be graded according to the CTCAE V.5.0. classification.

The occurrence of any of the following AEs during Cycle 1 (Day 1 – Day 28) will be considered a DLT, except for those AEs clearly related to disease progression or intercurrent illness.

Hematologic:

1. Grade 4 or greater hematologic toxicity (neutropenia, thrombocytopenia, or anemia)
2. Grade 3 febrile neutropenia (absolute neutrophil count [ANC] < 1000/mm³ with a single temperature of > 38.3°C (101°F) or a sustained temperature of ≥ 38°C (100.4°F) for > 1 hour)
3. Grade 3 thrombocytopenia with clinically significant bleeding

Non-hematologic:

1. Grade 2 or greater ocular toxicities leading to reduced visual acuity limiting ADL, glaucoma, retinal detachment, or retinal vascular disorder
2. NYHA class III or IV left ventricular dysfunction
3. Grade 3 or greater non-hematologic toxicity that is clinically significant with the following exceptions:
 - a. Toxicity (other than rash) that starts to resolve within 3 days of initiating optimal supportive care
 - b. Grade 3 rash that resolves to grade 1 or less within 7 days of initiating optimal supportive care
 - c. Grade 3 laboratory abnormalities that are not associated with clinical sequelae (e.g., isolated lactate dehydrogenase elevation) and resolves to Grade ≤1 within 3 days of initiating optimal supportive care
 - d. Grade 3 or 4 electrolyte laboratory abnormalities that last up to 72 hours, are not clinically complicated, and resolve spontaneously or respond to conventional medical interventions
 - e. Grade 3 or 4 amylase or lipase elevation that is not associated with symptoms or clinical manifestations of pancreatitis
 - f. Alopecia
4. Grade 4 non-hematologic toxicity, with the exception of those listed above, regardless of clinical significance or duration
5. Hy's law criteria (Grade ≥ 2 bilirubin in conjunction with grade ≥2 transaminase and without elevation of alkaline phosphatase)

In addition, clinically important or persistent toxicities not included above may also be considered a DLT at the discretion of the investigator after consultation with the SpringWorks physician.

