Any Grade \geq 3 event	Interrupt mirdametinib until resolution to Grade \leq 1. After resolution to Grade \leq 1, the Investigator may re-start mirdametinib at the next lower dose (see Table 5) or permanently discontinue mirdametinib, depending on the Investigator's benefit-risk assessment.
MUSCULOSKELETAL	
Grade \geq 3 muscle weakness (symptomatic and interfering with ADL).	Interrupt mirdametinib until resolution to Grade \leq 1. After resolution to Grade \leq 1, re-start mirdametinib at the next lower dose (see Table 5).
DERMATOLOGICAL	
Grade \geq 3 rash	Interrupt mirdametinib until resolution to Grade \leq 1. After resolution to Grade \leq 1, re-start mirdametinib at the next lower dose (see Table 5).
LVEF	
Grade 2 LVEF decrease (post-baseline LVEF of 40-49%)	If asymptomatic, interrupt mirdametinib until LVEF resolves to \geq 50%. Perform LVEF exams at least biweekly or more frequently at the Investigator's discretion until satisfactory resolution. After resolution to Grade \leq 1, re-start mirdametinib at the next lower dose (see Table 5).

	If symptomatic, permanently discontinue mirdametinib.
Grade 3 LVEF decrease (post-baseline LVEF of 20-39% or $\geq 20\%$ difference between the post-baseline vs. baseline LVEF)	If asymptomatic, interrupt mirdametinib and repeat LVEF exam in one week. If repeat exam shows persistent Grade 3 LVEF decrease, then permanently discontinue mirdametinib. If repeat exam shows Grade 2 LVEF decrease or better, then apply the guideline listed above for Grade 2 LVEF decrease. If symptomatic, permanently discontinue mirdametinib.
Grade 4 LVEF decrease (post-baseline LVEF $< 20\%$)	Permanently discontinue study treatment.
QTcF	

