Grade 3 AST or ALT increase (>5.0x to 20.0x ULN if baseline was normal; >5.0x to 20.0x baseline if baseline was abnormal)	Interrupt mirdametinib until resolution to Grade ≤1 (or Grade ≤2 if the subject has liver metastases). After resolution to Grade ≤1, re-start mirdametinib at the next lower dose (see Table 5).
Grade 4 AST or ALT increase (>20.0x ULN if baseline was normal; >20.0x baseline if baseline was abnormal)	Permanently discontinue mirdametinib
Potential DILI / Hy's Law (pending clinical adjudication)	
Total bilirubin increase ≥2.0x ULN and ALT or AST increase ≥3.0x ULN	Permanently discontinue mirdametinib. If clinical adjudication confirms DILI / Hy's Law, then report DILI as SAE.
OTHER	
Grade ≥ 3 hematologic toxicities or clinically significant Grade 2 hematologic abnormalities that do not resolve within 72 hours after initiation of medical management.	Interrupt dosing, after resolution to Grade ≤ 1, restart study treatment at the next lower dose following Table 5.
Grade ≥ 3 nonhematologic toxicity that is not controlled by optimal supportive medication.	Interrupt dosing; after resolution to Grade ≤ 1 or baseline, restart study treatment at the next lower dose following Error! Reference source not found.
Other Grade 2 toxicity that is subjectively intolerable (except alopecia) and not controlled by optimal supportive medication.	Interrupt dosing; after resolution to Grade ≤ 1 or baseline, restart study treatment at the same dose.
Recurrent subjectively intolerable toxicity (at least a week interruption on 2 occasions) that is not controlled by optimal supportive medication.	Interrupt dosing; after resolution to Grade ≤ 1 or baseline, restart study treatment at the next lower dose using Error! Reference source not found. If toxicity is still intolerable, permanently discontinue study treatment (unless otherwise discussed with the Principal Investigator).

ADL=activities of daily living; LVEF=left ventricular ejection fraction

In the event a dose reduction is required, the study treatment total daily dose will be reduced as shown in Table 5:

Memorial Sloan Kettering Cancer Center
 [name]
 [name]

Table 5 Mirdametinib Dose Reduction

Dose at the time of the event	Reduced dose
2 mg BID	1 mg BID
4 mg BID	2 mg BID
6 mg BID	4 mg BID

BID = twice daily

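### The 3+3 count drops and replaces patients who lose more than 20% of Cycle 1 doses to drug toxicity that is not a DLT, so it understates toxicity that prevents adequate dosing

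*Combined protocol and SAP*

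**What the plan says.** **Who counts.** Section 13.3 treats a patient as DLT-evaluable if she or he "received at least 45 of 56 [greater than 80%] doses of mirdametinib" or had a DLT, and Arm 1 also requires both fulvestrant doses. Section 14.1 defines the DLT Evaluable Population through "patients who receive at least 80% of planned total doses of mirdametinib in cycle 1", again with a DLT as the alternative. Section 4.2 asks Arm 1 patients to "complete Cycle 1 and receive at least 80% of doses at their assigned mirdametinib doses and all of their fulvestrant doses", and Arm 2 patients to "complete Cycle 1 and receive at least 80% of assigned drug doses, or if they exhibit a DLT in Cycle 1".

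**What happens to the rest.** Section 13.3: "Additional patients should be enrolled at the same dose level as necessary to ensure an adequate number of DLT-evaluable patients". None of these sections asks why doses were missed.

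**What is a DLT.** The first hematologic criterion in Section 15.3 is "Grade 4 or greater hematologic toxicity (neutropenia, thrombocytopenia, or anemia"). Below Grade 4, only febrile neutropenia and thrombocytopenia with significant bleeding qualify. No criterion concerns doses missed, held or reduced because of toxicity.

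**What forces doses to be missed.** Section 15.4 and Table 4 order holds, and in places permanent discontinuation, for related events. Several of these events are not on the 15.3 list.

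**The concern.** Evaluability depends on having taken the drug, and tolerability is one of the things that decides whether a patient takes it. A patient whose dosing is stopped by a related event short of a DLT leaves the count and is replaced by someone who may tolerate the level better. The exclusion is informative.

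The numbered rules in Section 4.2 set the RP2D from DLT counts in 3 to 6 patients, so one reclassified patient can reverse a decision. The chosen dose then goes into expansion cohorts of up to 28 (Arm 1) or 30 (Arm 2) patients each. Incidence of Cycle 1 DLTs is also part of the primary endpoint in Table 1.

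**Working it through.** **1. The plan's own figures.** Section 14.1 gives escalation probabilities of 0.9, 0.7, 0.5, 0.3 and 0.2 at true DLT risks of 0.1 to 0.5. The standard 3+3 formula is P(escalate) = (1-r)^3 + 3r(1-r)^2 × (1-r)^3. It gives 0.906, 0.709, 0.494, 0.309 and 0.172, which round to the stated values. The table takes r as given and does not address who is removed before r is estimated.

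**2. How much missed dosing removes a patient.** Continuous dosing plans 28 × 2 = 56 doses. 45/56 = 80.4% is evaluable and 44/56 = 78.6% is not, so 12 missed doses (6 days) suffice. A 7-day hold leaves 42/56 = 75%.

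**3. Events that stop dosing under 15.4 but are not DLTs under 15.3.**
- Grade 3 neutropenia without fever, or Grade 3 thrombocytopenia without significant bleeding: held to Grade 1 or better, and Table 4 provides for holds beyond 7 days.
- Grade 3 rash: Table 4 holds it to Grade 1 or better (the general text of 15.4 accepts Grade 2 for rash), while 15.3 exempts rash that reaches Grade 1 within 7 days.
- Grade 2 bilirubin: held to baseline, with holds beyond 7 days provided for.
- Intolerable Grade 2 toxicity not controlled by supportive medication: held to Grade 1 or baseline.
- Bilirubin at least 2x ULN with ALT or AST at least 3x ULN: permanent discontinuation. The Hy's law criterion in 15.3 requires that alkaline phosphatase is not raised. If it is raised and both values stay at Grade 2, no listed DLT criterion is met. The Table 4 sentence beginning "If clinical adjudication confirms DILI" leads to SAE reporting, not to a DLT.

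In Arm 1, Section 4.2 requires the 80% at the assigned dose, so an early dose reduction for toxicity could also remove a patient.

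**4. Effect on the count.** Let p be the probability of a protocol DLT and q the probability of losing more than 20% of doses to drug toxicity without a DLT. The documents give neither, so the values below are assumptions.
- Replaced, as planned: event rate p/(1-q).
- Counted as events: p+q.
- Kept as evaluable non-DLTs: p.

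p/(1-q) < p+q is equivalent to 0 < q(1-p-q), which holds whenever q > 0 and p+q < 1.

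Most levels expand to 6 after 0 or 1 DLT in 3. For these, P(at most 1 of 6) = (1-r)^6 + 6r(1-r)^5. With p = 0.20 and q = 0.15:
- Replaced: r = 0.20/0.85 = 0.235, giving 0.569.
- Counted: r = 0.35, giving 0.319.
- Kept as non-DLT: r = 0.20, giving 0.655.

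| p | q | p/(1-q) | p+q | Replaced | Counted | Kept as non-DLT |
|---|---|---|---|---|---|---|
| 0.10 | 0.05 | 0.105 | 0.15 | 0.875 | 0.776 | 0.886 |
| 0.10 | 0.10 | 0.111 | 0.20 | 0.863 | 0.655 | 0.886 |
| 0.10 | 0.20 | 0.125 | 0.30 | 0.833 | 0.420 | 0.886 |
| 0.20 | 0.05 | 0.211 | 0.25 | 0.630 | 0.534 | 0.655 |
| 0.20 | 0.10 | 0.222 | 0.30 | 0.601 | 0.420 | 0.655 |
| 0.20 | 0.15 | 0.235 | 0.35 | 0.569 | 0.319 | 0.655 |
| 0.20 | 0.20 | 0.250 | 0.40 | 0.534 | 0.233 | 0.655 |

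Arm 2 Dose Level 1 escalates on 0 of 3, so the formula in step 1 applies there. Replaced versus counted is 0.897 vs 0.814 at (0.10, 0.05) and 0.600 vs 0.309 at (0.20, 0.20).

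**5. How often it would arise.** The chance that at least one of the first six enrolled is dropped this way is 1-(1-q)^6: 27%, 47% and 74% at q = 0.05, 0.10 and 0.20.

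**The case against.** **Direction.** A reader might infer that the DLT rate itself is biased downward. The documents do not support that. Under 15.3 these patients are non-DLTs, so removing them raises the protocol-defined proportion (0.20 to 0.235 in the worked case) and lowers the chance of passing from 0.655 to 0.569. For the DLT as defined, replacement is the stricter rule. The lower figure of 0.319 appears only when every such patient is relabelled as an event. Relative to DLT risk under full dosing, the bias is downward only if the dropped patients' risk exceeds p/(1-q). That is plausible but not shown. This part of the objection stands and limits the point to toxicity that prevents adequate dosing.

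**Safeguards.** There are two. Section 15.3 lets the investigator, after consulting the manufacturer's physician, call other clinically important or persistent toxicities DLTs. Section 4.2 bases decisions also on the overall safety profile and on review of all available safety and PK data. Both could catch these patients. Neither requires it, and neither has a missed-dose trigger.

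**Reporting.** The patients' adverse events stay in the safety population (14.1, 14.3), so most of the primary endpoint is unaffected. Only the DLT component and the 3+3 decision are touched.

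**Fit to Cycle 1.** The Table 4 row reading "If asymptomatic, interrupt mirdametinib until LVEF resolves to" 50% looks like a natural example, but the first scheduled on-treatment echocardiogram is at Cycle 3, so it rarely applies. After Day 1, the only scheduled Cycle 1 blood draw is Day 15, which narrows the laboratory examples. A hold starting then still has 14 days in which to reach 6.

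**Size.** The rates are assumed and could be low. In the plexiform neurofibroma trials, 1 of 20 adults (interim data) and 5 of 19 patients needed dose reductions. Those figures are not limited to Cycle 1 and come from doses capped at 4 mg BID, in both trials on a 3-weeks-on, 1-week-off schedule. The range therefore includes q = 5%.

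**Conclusion.** The concern holds in a limited form. As written, the plan removes patients from the 3+3 count because the drug stopped them taking it, and replaces them automatically. The count then understates toxicity that prevents adequate dosing, but not the protocol-defined DLT proportion.

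Over the assumed ranges (p 10-20%, q 5-20%), P(at most 1 of 6) is about 0.53-0.88 with replacement and 0.23-0.78 if these patients counted as events. The gap runs from about 0.10 (0.875 vs 0.776 at p = 0.10, q = 0.05) to about 0.41 (0.833 vs 0.420 at p = 0.10, q = 0.20). It measures how much a decision depends on the handling of these patients. It does not show that the existing DLT estimate is wrong by that amount, and the true size is unknown. The calculation also assumes independent patients with the same p and q.

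**What to change.** - In Sections 13.3, 14.1 and 4.2, limit automatic replacement to patients who missed doses for reasons unrelated to study drug.
- At each 3+3 decision, list every patient below 80% because of a drug-related adverse event, with the event and the doses missed. Show the decision with and without these patients counted as not tolerating the level.
- The sponsor should reconcile the DLT list in 15.3 with the holds and discontinuations in 15.4, and state in advance how such patients enter the decision. Whether a given hold should be dose-limiting is a clinical choice for the sponsor, and this review takes no position on it.

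Cost: protocol wording and a short listing at each decision. Dose decisions may become somewhat more conservative.

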13.4 Evaluation of Tumor Response

13.4.1 Overview

The efficacy of both study arms will be evaluated by assessment of tumor response to treatment according to RECIST v1.1 [[Eisenhauer 2009](#)] per investigator assessment.

Response to treatment will be based on investigator evaluation of radiographic images. All radiographic images/scans at the time points specified as well as any unscheduled images/scans should be archived for potential future evaluation.

CT or MRI scans will be performed on each patient. Baseline images should encompass all areas of known predilection for metastasis of the disease under evaluation and should additionally investigate areas that may be involved based on signs and symptoms of individual patients. The imaging method used for the patient at screening will be used at each subsequent visit.

Any other sites at which new disease is suspected should also be appropriately imaged. If an unscheduled assessment is performed and the patient has not progressed, every attempt should be made to perform subsequent assessments at the scheduled visits while the patient remains on study drug.

